Study Protocol and Statistical Analysis Plan

Project Title:

Version Date:

Transitional rehabilitation in CABG patients

4-17-17

NCT number:

NCT03892460

**Principal
Investigator:**

[name]

Co-Investigator:

[name]

Grant Sponsor:

University of Vermont, College of Medicine, Department of Medicine

Summary:

Coronary artery bypass graft (CABG) surgery is a common surgical procedures and an important treatment option for coronary artery disease. As with any major surgical or medical procedure, the period of rest and recovery that follows is associated with cardiorespiratory and skeletal muscle deconditioning that can leave patients feeling weak and fatigued. Cardiac rehabilitation exercise training is recommended to recover lost strength and fitness. However, patients typically do not begin cardiac rehabilitation until 4-6 weeks following CABG surgery. Rehabilitative interventions to bridge the period between discharge following CABG surgery and the start of cardiac rehabilitation could improve patient cardiorespiratory and their ability to perform daily activities.

The goal of this research study is to understand whether an at-home exercise program started soon after CABG surgery, and continuing for 4 weeks following discharge from the hospital, can serve as a bridge between surgery and the start of cardiac rehabilitation to preserve physical function. Volunteers will be randomly assigned to receive neuromuscular electrical stimulation (NMES) of their quadriceps muscles or not to receive NMES (control group). Volunteers will be evaluated prior to CABG (Pre-surgery testing), upon discharge and 4 weeks Post-CABG surgery. Assessments will include measurements of physical function by the Short Physical Performance Battery and 6 min walk tests, as well as assessment of subjective physical functional capacity and quality of life using the Medical Outcomes Short form 36. Additionally, accelerometry will be used to monitor weight-bearing physical activity during the 4 week treatment phase.

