If successful, results from these studies will advance knowledge by providing proof-of-principle evidence for the utility of NMES to counter physical functional deterioration in the early, post-surgical period following CABG. Additionally, our findings may advance postoperative care of CABG patients by providing a clinical intervention to bridge a gap in rehabilitation services prior to entry into formal CR. Maintaining functional capacity in patients post-discharge may reduce the risk for re-hospitalization and progression towards disability. Greater functionality upon entry into CR may permit greater functional and health benefits from exercise during CR.

Purpose:

CR programs were initially developed to counter the deconditioning effects of medical and surgical interventions in cardiac patients and they have well-accepted health and survival benefits (1). Although CR is an important part of the care continuum (2), CABG patients typically do not start CR until ~4-6 wks after discharge (3). During this period, patients can experience further deterioration in physiological reserve, with increased risk for post-operative complications, readmission and development of physical disability (4-6). Whereas a large number of studies have focused on transitional care initiatives in medical and surgical cardiac populations to improve clinical outcomes and minimize costs (7), very few have focused on bridging this gap in physical rehabilitation care.

One reason for the absence of transitional rehabilitative care services in cardiac surgical patients is the inherent difficulty of intervening in a post-surgical population, as pain and limited mobility from surgical wounds diminishes motivation towards classical exercise. Moreover, reduced physical function related to surgery and hospitalization may render patients unable to perform basic activities of daily living at home, much less exercise. These hurdles represent a significant barrier to bridging the gap in rehabilitative care of cardiac surgical patients. Alternative exercise modalities that confer a training effect, but that do not have the physical requirements of classical aerobic or resistance training, could bridge this gap. Optimal candidates should induce an exercise training response, integrate easily into outpatient and home environments and be easy to use and inexpensive.

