NMES will be carried out bilaterally on the quadriceps using a portable stimulator (EMPI Continuum). Two adhesive electrodes will be affixed to the anterior surface of each thigh: ~1 cm distal to the inguinal crease and ~5 cm proximal to the patella, just lateral to the midline of the thigh to assure that it does not interfere with incisions for vein harvest. Symmetrical, biphasic pulses (400 μ s duration at 25 Hz) will be used, with a duty cycle of 25% (10 s on, 30 s off). Patients will be trained to conduct NMES sessions and will select stimulation intensities sufficient to cause visible muscle contractions below their pain threshold. Training in the use of the NMES device will begin within 96 hrs of transfer to the surgical step down unit. This training will consist of one session per day of ~15 min to familiarize the volunteer with the unit and the exercise/contraction stimulus. Upon discharge, NMES sessions will occur 5 d/wk once per day for 45 min per occasion (5 min low-intensity warm-up, 40 min higher-intensity stimulation) for 4 wks. This program is meant to mimic an aerobic-type exercise stimulus (8) and has been shown in heart failure patients to have functional benefits over a similar treatment period (9, 10). The 4 wk duration reflects the approximate average time that most CABG patients take to enter CR at our center. We acknowledge that the NMES training load is substantial, but have modeled this program on others that have shown morphological and functional effects in heart failure patients (11). At this exploratory stage, we feel that it is essential to use a stimulus that affects muscle size and function, with future studies modifying the NMES dose to establish a threshold that elicits a training effect with the highest subject

compliance rate. Daily logs and weekly phone contacts will be used to track compliance, and compliance will be covertly monitored using the device software.

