An individual research record will be kept on each volunteer in compliance with HIPAA standards. This record will contain identifying data, demographic information and results from all clinical research measurements and evaluations. The results of all testing will be kept confidential. All materials gathered in conjunction with the proposed studies will be used for research purposes only and will be available only to research personnel working on these studies, who have obtained proper training in human subjects research and privacy protection.

Statistical Analysis Plan:

Our primary goal is to assess changes in SPPB score and 6 MW between study groups to test whether NMES prevents the erosion of functionality from admission to 4 wk post-discharge (approximate time for starting CR). A general linear mixed model will be used, with group and time as fixed effects. The primary comparison will be between measures at admission and 4 wks post-discharge, as changes over this time period will reflect the effects of the surgery, post-op recovery and post-discharge/pre-CR periods. Because function may be impaired pre-surgery due to angina/dyspnea/etc, post-surgery measures may be a better indicator of functional capacity and we have the ability to calculate the changes in these measures from Discharge to 4 wks post-surgery. We will assess QOL by questionnaire and activity by accelerometry as secondary outcomes to determine if NMES improves patient-reported QOL and free-living daily activity, respectively, vs. usual care. Covariates (eg, length of stay, time to start of CR, admission SPPB, etc) can be included in the models to control for potential confounders that might differ by group in the event that randomization fails to equate groups for these variables.

DRUG AND DEVICE INFORMATION

Drug (s) **Not applicable**

Device (s) **Not applicable**

The interventional device used in this study: EMPI Continuum complete electrotherapy system has received FDA approval (501K: K093324) for retarding disuse-related atrophy, which we believe is one of the primary mechanisms whereby CABG patients become more functional disabled in the early, post-surgical period. That is, muscle disuse secondary to pain, limited range of motion and muscle weakness causes skeletal muscle fiber atrophy and weakness, as well as mitochondrial rarefaction and dysfunction that further impair physical fitness.

Is it FDA approved:

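### Covariates may enter the models when the arms look different, with no criterion and an open list that names time to start of cardiac rehabilitation, a variable that arises after allocation

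*Combined protocol and SAP*

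**What the plan says.** The Statistical Analysis Plan section describes one model, for SPPB and 6MW: "A general linear mixed model will be used, with group and time as fixed effects". It adds that "The primary comparison will be between measures at admission and 4 wks post-discharge". It then offers an optional clause, "Covariates (eg, length of stay, time to start of CR, admission SPPB, etc) can be included in the models to control for potential confounders", to be used "in the event that randomization fails to equate groups for these variables". The documents give no test or threshold for imbalance, no closed list, no time for the decision, and no statement of which result is primary if adjusted and unadjusted analyses disagree. Age and sex are stratification factors under Study Design but are not named as model terms.

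Four places bear on when CR starts:

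- Statistical Analysis Plan: the outcome time is "4 wk post-discharge (approximate time for starting CR".
- Treatment phase: "The 4 wk duration reflects the approximate average time that most CABG patients take to enter CR at our center".
- Summary: "patients typically do not begin cardiac rehabilitation until 4-6 weeks following CABG surgery".
- Purpose: "CABG patients typically do not start CR until ~4-6 wks after discharge".

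No procedure listed under Study Design, Procedures or Questionnaires records the date on which CR starts, and the last visit is the 4-week one.

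**The concern.** Randomisation balances, on average, only what exists before allocation. Time to start of CR does not exist then. All four statements place it weeks later, at about or after the outcome visit. Some patients may start before that visit, but the variable is post-allocation either way. If the arms differ on it, the cause is chance or NMES itself. The plan's own rationale links functional recovery with CR, so an effect of NMES on CR start is plausible. The clause would allow that effect to be handled as a confounder.

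The second problem is the trigger. With no criterion and an open list, the adjustment set is settled after the arms have been compared. A reader of the results could not tell which model had been planned.

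**Working it through.** **Figures in the plan.** Study Design gives 18 per arm, so 36 completers. Number of Subjects gives 48 enrolled at 25% attrition: 36/(1 − 0.25) = 48, which reproduces. The plan gives no SD, correlation, effect size or alpha, so every such value below is an assumption.

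**Assumptions.** Pre-surgery and 4-week scores have SD 1 and correlation ρ = 0.6. The true effect at 4 weeks is 0.80 SD. Time to CR, T, has within-arm SD 1.

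**Step 1: does the way the covariate enters matter?** Yes. A patient-level covariate with the same coefficient at every visit cancels from each patient's change. With complete data the group-by-time contrast therefore cannot move. In a test dataset (18 per arm, slope 0.5) a random-intercept model gave 0.8901, SE 0.2422, both with and without T. An unstructured covariance fit gave 0.8007 both ways. Adding T by time moved these to 0.6808 and 0.7099.

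**Step 2: T follows recovery.** Let T = −s × (4-week score) + noise. Within arm, the slope of change on T is −s(1 − ρ), and the arms differ in T by −0.8s. The adjusted change is then 0.8 − 0.8s²(1 − ρ) = 0.8[1 − s²(1 − ρ)].

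| s | Always adjusted | Trigger p<0.10 fires | Average with trigger |
|---|---|---|---|
| 0.2 | 0.8(1 − 0.016) = 0.787 | 14% | 0.793 |
| 0.3 | 0.8(1 − 0.036) = 0.771 | 18% | 0.785 |
| 0.5 | 0.8(1 − 0.100) = 0.720 | 32% | 0.754 |

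The last two columns are simulated (40,000 runs). The distortion is larger in two other settings:

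- If the 4-week score is adjusted for both pre-surgery score and T, the estimate is 0.8[1 − s²(1 − ρ²)/(1 − s²ρ²)] = 0.78, 0.75, 0.66.
- For an outcome with no baseline it is 0.8(1 − s²) = 0.77, 0.73, 0.60.

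**Step 3: NMES itself shifts CR start.** Let NMES move T by a SD, and let T correlate r with change within arm. The SD of change is √(2(1 − ρ)) = √0.8 = 0.894, so the adjusted change is 0.8 − r·a·0.894. With r = −0.3:

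- a = −0.3 (earlier start): 0.8 − 0.080 = 0.72.
- a = +0.3 (later start): 0.8 + 0.080 = 0.88.

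Averaged over a p<0.10 trigger, which fires in 23% of trials, these become 0.76 and 0.84. The bias can go either way.

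**Step 4: type I error when the covariate set is chosen after looking.** Under the null (20,000 runs per setting; ρ 0.5 to 0.7, s 0.2 to 0.5, length of stay correlated −0.3 with pre-surgery SPPB), the most favourable subset of the imbalanced covariates is taken, in a change-score type of analysis.

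| Definition of imbalance | Type I error |
|---|---|
| p<0.05 | 5.0% to 5.5% |
| p<0.10 | 5.2% to 5.8% |
| p<0.20 | 5.8% to 6.4% |
| standardised difference >0.25 | 6.9% to 7.8% |

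Entering every covariate with p<0.10 mechanically gives 3.8% to 4.3%, slightly conservative.

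**Step 5: precision of a fixed baseline adjustment.** If the 4-week SD is k times the pre-surgery SD, the large-sample variance ratio (baseline-adjusted over change score) is k²(1 − ρ²)/(k² + 1 − 2ρk). At ρ = 0.6 this is 0.64/0.80 = 0.80 for k = 1 and 1.0816/1.13 = 0.957 for k = 1.3. At 18 per arm with three covariates, for ρ 0.5, 0.6 and 0.7, the ratios are 0.83, 0.88 and 0.93 (k = 1) and 1.00, 1.06 and 1.09 (k = 1.3).

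**The case against.** The strongest defence is that the clause is permissive, conditional and secondary. Group and time remain the default, and adjustment is something the team may do. The study is small and described as exploratory. The simplest reading of including a covariate in a mixed model is a plain fixed effect, and Step 1 shows that this leaves the primary contrast untouched with complete data. CR start may not even be recorded. All of this stands, and it limits the size of the point. It does not remove it, because the plan does not say how covariates enter, a primary hypothesis is tested, and the clause also covers outcomes without a baseline.

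Four stronger readings are tempting, and the documents do not support them:

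- *The primary estimate will be biased.* The text only permits the adjustment, and one natural way of doing it has no effect on the contrast.
- *Type I error reaches 10% to 18%.* Free choice among all subsets of three to five covariates gives 10.4% to 17.8%, but that admits covariates that are not imbalanced. The clause requires imbalance.
- *Length of stay is equally invalid.* That holds only if allocation precedes discharge. Study Design lists the randomised Treatment Phase after Discharge testing, while the Treatment phase text starts NMES training in the step-down unit. These must be reconciled before anything firm is said. The exclusion of complicated stays beyond 7 days also narrows the variable's range.
- *Leaving out pre-surgery SPPB, age or sex invalidates the analysis.* It costs precision, not validity.

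**Conclusion.** The defect is real: adjustment is triggered by observed imbalance without a criterion, from an open list that includes a variable arising after allocation. Its consequence is conditional. It is nil for the group-by-time contrast if the covariate is a plain fixed effect and data are complete. Distortion arises if the covariate enters by time, in a change-score or 4-week model, through a group main effect, or for an outcome without a baseline. In the change-score case the loss is at most 0.08 SD of an assumed 0.80 over the slopes tried, and 0.05 SD or less on average with a p<0.10 trigger. It is larger where there is no baseline, and its direction is not assured. These sizes rest wholly on assumed slopes, correlations and effect. Type I inflation is modest.

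This is a cheap improvement, between worth considering and should be done. Prespecification is the main reason for it, and precision comes second.

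**What to change.** Replace the covariate sentence of the Statistical Analysis Plan with:

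> The SPPB comparison of arms at 4 weeks is adjusted for pre-surgery SPPB and for the stratification factors age and sex, whatever the observed balance. No variable that arises after randomisation is a covariate in the primary or secondary treatment comparisons; this includes time to start of CR, and length of stay if randomisation precedes discharge. Any other covariate model is a labelled sensitivity analysis restricted to pre-randomisation variables.

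Adjust QOL for its own pre-surgery score, age and sex. Adjust 6MW and activity for age and sex; the Procedures section excludes 6MW from Pre-surgery testing, although the opening of Study Design suggests otherwise. State when randomisation occurs relative to Discharge testing. The change from admission to 4 weeks can still be reported within each arm.

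The cost is wording only, with no new visits, patients or data. The adjusted model uses about three degrees of freedom (36 − 2 = 34 falls to 31). If the 4-week SD is well above the pre-surgery SD there is no precision gain: at a ratio of 1.3 the variance is equal to the change score's or up to about 9% larger.

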We will use a prospective design, in which patients scheduled for elective CABG will be recruited and evaluated prior to CABG (Pre-surgery) and upon discharge (Discharge) for physical function (SPPB Testing and 6 min walk). Patients will be recruited for this study during the normal process of clinical recruitment for cardiac rehabilitation. This includes patients from cardiothoracic consultation lists and/or those scheduled for elective CABG. In some instances, we will identify patients from cardiothoracic consultation lists who are or will be scheduled for CABG, but are not on the surgical unit. We will contact these patients by phone regarding participation in cardiac rehabilitation and, at that time, introduce this research study. Patients will be randomized (1:1) to NMES or control intervention (n=18/group; Treatment Phase), with stratification for age and sex. Following completion of the 4 wk intervention,

volunteers will undergo Post- Testing, which will be identical to Pre-surgery and Discharge testing. Each protocol phase is described below.

Pre-surgery testing Baseline testing will occur prior to CABG surgery and at discharge and consist of functional assessment by the SPPB and a quality of life (QOL) questionnaire (MOS-SF36). Tests are described below.

Discharge testing will repeat Pre-surgery testing and include a 6MW. At this time, volunteers will receive an accelerometer, which will be worn during three (3) 5-day periods during the Treatment phase.

Treatment Phase

Patients will be randomized (1:1) to NMES or control intervention and will continue in this Treatment phase until 4 weeks post-CABG surgery.

4 wk Post-surgery testing will be identical to Discharge testing.

Procedures:

All of the procedures and interventions on volunteers recruited for these studies are carried out solely for research purposes, as none are part of standard therapy in CABG patients.

Physiological Testing (during Pre-surgery (excluding 6 MW), Discharge and 4 wk Post-surgery testing)

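### The SAP does not say how admission SPPB enters the mixed model; added as a main effect while admission remains an outcome visit, it would not adjust the primary change contrast

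*Combined protocol and SAP*

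**What the plan says.** The points below come from the Statistical Analysis Plan section unless another section is named.

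- Goal: "Our primary goal is to assess changes in SPPB score and 6 MW between study groups".
- Model: "A general linear mixed model will be used, with group and time as fixed effects". No group-by-time term and no covariance structure is stated.
- Primary contrast: "The primary comparison will be between measures at admission and 4 wks post-discharge". Admission SPPB is therefore one of the outcome visits. I read admission as the Pre-surgery test of the Study Design section.
- Covariates: "Covariates (eg, length of stay, time to start of CR, admission SPPB, etc) can be included in the models to control for potential confounders". The trigger is conditional: "in the event that randomization fails to equate groups for these variables". The section does not say whether a covariate enters as a main effect or by visit, or whether the admission visit leaves the outcomes when it becomes a covariate.
- Alternative contrast: "we have the ability to calculate the changes in these measures from Discharge to 4 wks post-surgery".
- Study Design section: "Patients will be randomized (1:1) to NMES or control intervention (n=18/group; Treatment Phase), with stratification for age and sex". SPPB is not a stratification factor, so its balance at admission is left to chance.

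**The concern.** A patient-level covariate entered as a main effect shifts all of that patient's visits by the same amount. The primary quantity is a within-patient change compared between arms, and a constant shift drops out of a change. Adding admission SPPB in this way, which is the most natural reading of including it in the model, would leave the primary SPPB estimate where it was.

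Two things are at stake. First, if the arms differ at admission, the report could say that the difference was controlled for while the estimate still carries it. Second, a small trial would pass over the precision that a working baseline adjustment can give from data it already collects.

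**Working it through.** **The plan's own figure.** The Number of Subjects section enrolls 48 so that 36 complete with 25% attrition: 36/(1 - 0.25) = 48, which reproduces, and 36 = 2 x 18. No SPPB SD, correlation, target effect, alpha or power is given. Every size below therefore rests on assumptions; the cancellation itself does not.

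**Step 1: the algebra.** Let m(g,t) be the mean for arm g at visit t, and let x be admission SPPB with slope b common to all visits. With complete data the fitted value is m(g,t) = observed mean(g,t) - b x mean x(g). The primary contrast is

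[m(NMES, 4 wk) - m(NMES, adm)] - [m(control, 4 wk) - m(control, adm)].

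The term b x mean x(g) appears once with each sign within each arm and cancels, leaving the raw difference in change. The same cancellation applies to any main-effect patient-level covariate in any complete-data change contrast, including Discharge to 4 weeks.

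**Step 2: numerical check, complete data.** Generalised least squares with 200 random 3 x 3 covariance matrices gave contrasts with and without the covariate that differed by less than 1e-11. REML random-intercept fits used 18 per arm, 3 visits and 60 datasets per correlation, with assumed SD 2, a 1-point admission imbalance and a true effect of 1.0. Some of these fits gave convergence or boundary warnings; the least-squares check does not depend on them.

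| Correlation | No covariate | Main effect added | By-visit term, or covariate only |
|---|---|---|---|
| 0.4 | 0.45 | 0.45 | 1.05 |
| 0.6 | 0.59 | 0.59 | 1.02 |
| 0.8 | 0.76 | 0.76 | 0.97 |

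The standard errors of the first two fits differ by at most 0.006 (0.729 against 0.723).

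**Step 3: missing 4-week visits.** With 9 of 36 missing at random, adding the main effect moved the estimate by 0.06 to 0.10 points on average (maximum 0.35). A second simulation used 24 per arm, 25% missing at random, 1,500 trials per correlation and known compound-symmetry covariance. The regression of the estimate on the admission imbalance was -0.66, -0.50 and -0.31 at rho 0.3, 0.5 and 0.7, both without and with the covariate. The movement is noise, not correction.

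**Step 4: group and time main effects only, as literally listed.** Here the group coefficient does move, from 0.98/1.06/1.22 to 0.38/0.35/0.37 at correlations 0.4/0.6/0.8. It is an average over visits that includes admission, not the change contrast. A 1-point effect present at one of three visits averages to 1/3 = 0.33.

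**Step 5: size of the uncorrected shift.** Per point by which NMES starts higher, the shift is -(1 - slope), with slope = rho x SD(4 wk)/SD(admission).

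- Equal SDs: rho 0.3, 0.5, 0.7 give -0.7, -0.5, -0.3.
- SD ratio 1.4, rho 0.7: slope = 0.98, shift = -0.02.
- Assumed SD 2, 18 per arm: the chance admission difference has SD 2 x sqrt(2/18) = 0.67 points, so at rho 0.5 with equal SDs the shift has SD 0.5 x 0.67 = 0.33 points.

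**Step 6: precision.** With equal SDs, the variance of the adjusted contrast relative to the change score is (1 - rho^2)/[2(1 - rho)] = (1 + rho)/2, that is 0.65, 0.75 and 0.85 at rho 0.3, 0.5 and 0.7. Simulated standard errors in SD units (change, then adjusted) were 0.392 and 0.320, 0.332 and 0.290, 0.257 and 0.239: reductions of 18%, 13% and 7%. With SD ratio k the variance ratio is k^2(1 - rho^2)/(1 + k^2 - 2 rho k). At k = 1.4 and rho 0.7 this is 0.9996/1.00, so almost nothing is gained.

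**The case against.** The strongest reply is that the SAP never commits to a main effect. An admission SPPB-by-visit term, or moving admission from the outcomes to the covariates, also fits its wording, and either one corrects the imbalance (last column of the table). The arm-by-visit contrast behind the cancellation is likewise supplied by the reader: it follows naturally from comparing changes between groups, but the SAP lists only group and time. Exact invariance also needs complete data, which a plan allowing for 25% attrition does not expect. All of this stands. The defect is under-specification, and a reader who infers that the SAP's adjustment is bound to correct nothing goes further than the text allows.

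Three further limits also stand:

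- Allocation is randomized, so a change-score contrast is unbiased over randomization and is a legitimate primary analysis in a study that describes itself as exploratory. The shift is conditional on the imbalance that happens to occur.
- The -(1 - rho) and (1 + rho)/2 figures require equal SDs at the two visits.
- The covariate sentence also serves other outcomes. Accelerometers are first issued at Discharge, so activity has no admission value, and for an arm difference in activity level a main-effect admission SPPB adjusts normally. Striking it from every model would lose that.

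What the reply does not do is rescue the main-effect reading. Missing data bring no systematic correction, and the literal group-plus-time model moves a coefficient that is not the primary contrast.

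**Conclusion.** The concern holds in conditional form. The SAP gives admission SPPB two roles in one model and leaves its form open. If it enters as a main effect, with admission kept as an outcome and an arm-by-visit contrast, the complete-data primary estimate is unchanged to the last digit, and attrition adds only small unsystematic movement. That result is algebraic.

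The size is not known from the documents. Under equal SDs and assumed correlations of 0.3 to 0.7, the uncorrected shift is 0.7 to 0.3 points per point of imbalance, against the arm that starts higher. It lies closer to zero if the 4-week SD is larger, and is near nil at a ratio of 1.4 with rho 0.7. The precision gain is illustrative in the same way.

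A reader might also infer that the planned primary estimate is biased as such. The documents do not support that: the bias exists only given an observed imbalance, which is the situation the SAP's covariate sentence sets out to handle. The point should be fixed before analysis because the remedy is cheap and the present wording permits an adjustment in name only.

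**What to change.** For the SPPB model, prespecify one of the following, to be used whatever imbalance is observed:

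- (a) Discharge and 4-week SPPB as outcomes, with visit, arm-by-visit and admission SPPB-by-visit terms; or
- (b) all three visits as outcomes, with visit and arm-by-visit terms and the admission mean constrained to be equal in the two arms.

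In either case, name the adjusted arm difference at 4 weeks as the primary estimate and state the covariance structure. Remove admission SPPB from the optional additive covariates for the SPPB change model only. Keep it available for outcomes with no admission value, such as accelerometry. Give any other baseline covariate used in a change model a visit interaction.

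The cost is SAP wording and about one degree of freedom per visit. No new data are needed.

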The goal of this application is to explore the utility of neuromuscular electrical stimulation (NMES) to counter the early, post-surgical deterioration in physical functional capacity. We chose NMES because it permits non-volitional initiation of muscle contractions that can produce an exercise training response similar to classical exercise training, with near comparable effects. We will test the ability of NMES to preserve physical function, as measured by the Short Physical Performance Battery (SPPB), a metric whose change in the first month post-hospitalization has been shown to predict re-hospitalization and death and that is validated for use in physically compromised elderly populations. We will also assess 6-minute walk (6MW) performance as a secondary outcome, a metric that is commonly used for FDA approval of various interventions that seek to improve physical function/fitness. Our rationale for the proposed studies is that interventions directed towards preventing deleterious skeletal muscle changes during this period and maintaining functional capacity will enhance the effects of CR to improve functionality and future cardiovascular risk. We will accomplish these goals using a randomized, controlled design. Based on our preliminary data, we hypothesize that NMES will prevent deleterious reductions in physical function by preserving skeletal muscle size function. To address this hypothesis, we propose a single aim:

Aim: Define the utility of NMES to preserve or increase physical functional capacity in patients during the period following CABG and prior to entry into CR.

Primary Clinical Outcome: NMES will diminish CABG-induced erosion of physical functional capacity, as assessed by the SPPB.

Secondary Clinical Outcome: NMES will diminish CABG-induced erosion of physical functional capacity, as assessed by the 6MW.

METHODS AND PROCEDURES

Study Design:

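### 6MW has no pre-surgery value under the specific test schedule, and the SAP does not commit to adjusting its 4-week comparison for Pre-surgery SPPB, so precision may be lost

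*Combined protocol and SAP*

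**What the plan says.** Objectives gives 6MW a named role: "Secondary Clinical Outcome: NMES will diminish CABG-induced erosion of physical functional capacity, as assessed by the 6MW".

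The combined document is not consistent on when 6MW is measured.

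- Three statements leave it out before surgery. Under Study Design, Pre-surgery testing consists of "functional assessment by the SPPB and a quality of life (QOL) questionnaire (MOS-SF36". The next paragraph says "Discharge testing will repeat Pre-surgery testing and include a 6MW". The Procedures heading reads "Physiological Testing (during Pre-surgery (excluding 6 MW), Discharge and 4 wk Post-surgery testing".
- The opening sentence of Study Design points the other way. It has patients "evaluated prior to CABG (Pre-surgery) and upon discharge (Discharge) for physical function (SPPB Testing and 6 min walk".

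The Statistical Analysis Plan specifies a general linear mixed model with group and time as fixed effects. Its main comparison, for SPPB and 6MW alike, runs from admission to 4 weeks after discharge. Change from Discharge to 4 weeks is mentioned as something the team is able to calculate. On covariates it says "Covariates (eg, length of stay, time to start of CR, admission SPPB, etc) can be included in the models to control for potential confounders", and the trigger is "in the event that randomization fails to equate groups for these variables". It gives no criterion for that failure.

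The Treatment phase text under Procedures starts NMES training within 96 hours of transfer to the step-down unit, which is before discharge.

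**The concern.** If the specific schedule is right, and admission (which the SAP does not define) means Pre-surgery, the SAP's main comparison has no starting value for 6MW. Two routes remain. One is the change from Discharge, but the Discharge walk follows the start of NMES training, so any effect already present at discharge is subtracted out. The other is a between-arm comparison at 4 weeks. That captures everything since allocation, but it carries between-patient differences in function that predate surgery.

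Pre-surgery SPPB could absorb part of those differences in the 4-week comparison. It is already collected, it precedes allocation, and it contains a 4-metre walk and chair stands. In a randomised trial the precision gained from a prognostic baseline covariate does not depend on whether the arms happen to look unbalanced. An imbalance trigger without a criterion makes its use both uncertain and data-driven. With 36 planned completers, precision on the named secondary outcome is limited.

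**Working it through.** **The plan's own figure.** Number of Subjects enrols 48 to obtain 36 completers at 25% attrition: 36 / (1 − 0.25) = 48. This reproduces, and 36 = 2 × 18 per arm. The documents give no alpha, power, effect size, SD or correlation, so the precision loss cannot be derived from them alone. The calculations below assume a two-sided 5% level, equal variances and complete data, and use SD units.

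**Between-arm contrast on 4-week 6MW.** Let ρ be the correlation of Pre-surgery SPPB with 4-week 6MW (assumed).

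- Unadjusted half-width at the true SD: t(34 df) × √(2/18) = 2.032 × 0.333 = 0.677. The sample SD averages slightly below the true SD, by a factor of about 1 − 1/(4 × 34) = 0.993. The mean half-width is then about 0.67, which simulation confirms.
- Adjusted variance factor with N = 36: (1 − ρ²) × (N − 3)/(N − 4) = (1 − ρ²) × 33/32.
- Adjusted half-width: 2.035 × 0.333 × √(variance factor) × (1 − 1/(4 × 33)).

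| Assumed ρ | Variance factor | Mean 95% CI half-width (SD) |
|---|---|---|
| no adjustment | 1.00 | 0.67 |
| 0 | 1.03 | 0.68 |
| 0.17 | 1.00 | 0.67 |
| 0.3 | 0.94 | 0.65 |
| 0.5 | 0.77 | 0.59 |
| 0.7 | 0.53 | 0.49 |

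Break-even is where (1 − ρ²) × 33/32 = 1, so ρ = √(1/33) = 0.17.

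**Discharge-to-4-week change in 6MW.** Let r be the correlation between the two 6MW values (assumed).

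- The SD of the change is √(2(1 − r)). At r = 0.7 this is 0.775, giving a half-width of 0.67 × 0.775 = 0.52 SD. That is tighter than the 0.59 SD for the SPPB-adjusted 4-week contrast at ρ = 0.5.
- Ignoring the degree-of-freedom cost, the change is the tighter contrast when 2(1 − r) < 1 − ρ², that is r > (1 + ρ²)/2. For ρ of 0.3, 0.5 and 0.7 the thresholds are about 0.55, 0.63 and 0.75.
- SPPB's correlation with the change is (ρ at 4 weeks − ρ at Discharge) / √(2(1 − r)). If the two are equal it is zero and SPPB gains nothing. If they differ by 0.1 to 0.2, with r of 0.5 or 0.7, the variance falls by about 1% to 7% before the degree-of-freedom cost.

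**Simulation check** (8,000 trials, 18 per arm, SPPB correlation 0.5 with both walks, r = 0.7). The SD of the group estimate for the 4-week value falls from 0.330 to 0.290 with SPPB. For the change it goes from 0.259 to 0.263.

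**The case against.** The strongest reply is that the SAP never plans a bare comparison of 4-week 6MW. It speaks of changes, puts time in the model and mentions the Discharge-to-4-week change, which already removes stable differences between patients. Against that contrast SPPB gains almost nothing, and a 4-week model with SPPB can be the less precise of the two. This stands as far as precision goes, and it is why the change should be kept. It does not settle the matter. The change starts after in-hospital training has begun, so it answers a narrower question than the SAP's comparison from admission, and the SAP offers it only as a possibility. The in-hospital sessions are described as short and for familiarisation, so the effect subtracted may be small, but the documents do not quantify it.

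Several stronger readings are tempting, and the documents do not support them.

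- A reader might infer that the SAP discards Pre-surgery SPPB. It permits it; what is missing is a commitment.
- A reader might take SPPB as the only pre-surgery information on function. MOS-SF36 is also completed then and covers subjective physical function. SPPB is the only performance-based measure.
- A reader might take the absence of a pre-surgery 6MW as settled. The opening sentence of Study Design contradicts it.
- A reader might state the precision loss as fact. The SAP itself notes that pre-surgery function may be impaired by angina or dyspnoea, which could weaken the correlation, and below about 0.17 adjustment slightly widens the interval.

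The Risks section also lets patients skip activities they cannot do, so a complete Pre-surgery SPPB for everyone is an assumption.

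**Conclusion.** The point holds in a limited form. Under the specific schedule, the SAP's comparison from admission cannot be computed for 6MW, and the only computable change begins at a visit after NMES training has started. That allocation precedes Discharge is inferred from the in-hospital training. For the between-arm contrast at 4 weeks, leaving SPPB to an undefined imbalance trigger may cost precision. At assumed correlations of 0.3, 0.5 and 0.7, omitting it forgoes variance reductions of about 6%, 23% and 47%. At zero correlation, including it would widen the half-width by only about 0.01 SD. No bias is shown, and the text on NMES calls this an exploratory stage. This is an inexpensive improvement to a secondary analysis and does not threaten the trial's main result.

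**What to change.** In the Statistical Analysis Plan, replace the imbalance trigger for SPPB with: 'The 6MW mixed model will always include Pre-surgery SPPB and its interaction with time, whatever the observed balance, and the arms will be compared at 4 weeks.' Comparing the arms at 4 weeks also needs a group-by-time term, which the SAP does not list. The SPPB-by-time term lets the SPPB slope differ between visits; a main effect alone would cancel out of any change contrast.

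Keep the Discharge-to-4-week 6MW change as a supporting analysis, since it can be more precise when the two walks correlate strongly. State that it starts after in-hospital training and that SPPB adds little or nothing to it.

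Reconcile the opening sentence of Study Design with the specific schedule, and define admission. If 6MW is in fact measured before surgery, the comparison from admission becomes computable and this point should be revisited.

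The SPPB terms cost one or two degrees of freedom, with a slightly wider interval if the correlation is below about 0.17. No new visits, measurements or patients are needed.
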